14.2.3 Additional analyses

Additional analyses may involve the analysis of prognostic factors, e.g. ISS stage, FISH analysis, molecular analysis and imaging parameters [PET-CT and MRI], with respect to response rate, PFS, and OS. Logistic and Cox regression could be used for this purpose. To include all patients in (multivariate) analyses, a multiple imputation algorithm will be used to impute missing covariate values if applicable. Before any additional analysis will be performed, a separate analysis plan will be discussed with the PI. Any such analysis should, however, be considered as exploratory, i.e. hypothesis generating, and not confirmatory.

14.2.4 Statistical analysis plan (SAP)

Before the final analysis, a SAP will be prepared by the trial statistician and approved by the principal investigator. It will describe in detail the analyses to be performed. Deviations from the analyses as specified in par. 14.2.1-14.2.3 will be discussed with the study coordinators and can only affect the exploratory analyses, but not the primary (confirmatory) analysis on which the sample size is based. All analyses except the primary analysis should be considered as hypothesis-generating only.

14.3 Interim analysis

One interim analysis is planned, primarily to describe adverse events observed during induction therapy. This will be done when data of the first 20 registered patients regarding cycles 1-4 are available. The accrual will not be discontinued while waiting for these data. Results of the interim analysis will be presented confidentially to an independent data and safety monitoring board (DSMB). Only if the DSBM recommends that the study should be stopped or modified, the results will be made public to the principal investigators for further decisions. The DSMB is free in its public recommendations to the study coordinators and the confidential recommendations to the study statistician. For the interim analysis a detailed report will be generated and presented to the DSMB. It will include the number of entered patients and at that time evaluable patients, treatment given, and

incidence of SAE's and other adverse events and infections by grade. Adverse events will be described by summary table broken by site, CTCAE grade and relation to trial treatment. The study will be closely and sequentially monitored before the interim analysis. Monitoring will be based on the reported SAE's, which are not subjected to data delay. In addition, a separate report on the incidence of SAE's and other adverse events and infections, as described before, will be sent to the DSMB once a year. Again, the DSMB is free in her public recommendations to the study coordinators and the confidential recommendations to the study statistician.

14.4 Statistical analysis of the quality of life assessement

All patients with the baseline and at least one follow-up QoL questionnaire, separately for QLQ-C30 and QLQ-MY20, will be included in the analysis, The main purpose will be to describe QoL during induction chemotherapy and maintenance or placebo. QoL after randomization will also be summarized separately for both randomized groups. For randomized patients, the QoL after the last induction chemotherapy will then be considered as baseline. To evaluate the difference in QoL between the two randomization arms with respect to the multi-item scales of the QLQ-C30 and QLQ-MY20, the repeated measures may be analyzed separately using mixed ANOVA models, and the single items using (ordinal) logistic regression with random effects. However, the limited number of randomized patients implies limited power, which might hamper firm conclusions.

15 Registration and Randomization

15.1 Regulatory Documentation

Required regulatory and administrative documents must be provided to the HOVON Data Center before shipment of study drug and before enrolment of the first patient. This will always include an Ethics Committee approval for the investigational site. The HOVON Data Center will provide each investigator with an overview of the required documents. Each investigational site will be notified when all requirements are met and enrolment can start

15.2 Registration and Randomization

15.2.1 Registration

Eligible patients should be registered before start of treatment. Patients need to be registered at the HOVON Data Center by one of the following options:

◆ Trial Online Process (TOP, https://www.hdc.hovon.nl/top). A logon to TOP can be requested at the HOVON Data Center for participants.

- By faxing the completed registration/randomization CRF [name] Monday through Friday, from 09:00 to 17:00 CET
- ♦ By [contact] Monday through Friday, from 09:00 to 17:00 CET

The following information will be requested at registration:

- Protocol number
- Institution name
- Name of caller/responsible investigator
- ♦ Sex
- Age at date of registration
- Date written informed consent
- Specific items patient gives consent for (see ICF)
- Eligibility criteria

Specific items:

'Risk Management Program' discussed with patient

All eligibility criteria will be checked with a checklist.

Each patient will be given a unique patient study number (a sequence number by order of enrolment in the trial). Patient study number will be given immediately by TOP or phone and confirmed by fax or email.

Local Patient Code is a code assigned to the patient by the investigational site for local administrative purposes. The code may be up to 8 characters long (letters and numbers allowed). The code should be in compliance with privacy regulations. It should not contain identifying data, such as patient initials or the complete hospital record number. The local code will be visible in the confirmation messages sent by TOP to local participants after registration of the patient. The key to this local patient code should only be accessible by the local investigator and the local trial staff. Using or entering a local patient code is not obligatory.

15.2.2 Randomization

All patients eligible for randomization can be randomized at the HOVON Data Center by web (as described above)

The following information will be required:

- Protocol number
- Patient's study number
- Eligibility criteria

Actual dose of ixazomib given during last induction cycle

Patients will be randomized, stratified by center and response ((s)CR vs VGPR vs PR) with a minimization procedure, ensuring balance within each stratum and overall balance.

The patient study number and the result of randomization will be communicated by the HOVON Data Center by email to the pharmacy of VU University Medical Center. Ixazomib citrate or placebo will be sent for the randomized patient to the pharmacy of the site. The result of the randomization will not be conferred to caregivers, patients, or their representatives until the end of the trial.

15.3 Unblinding procedure

The protocol treatment will be preferably unblinded after completion of the trial. While the safety of patients should always take priority, maintenance of blinding is crucial to the integrity of a double-blind trial. Before this planned unblinding, the blind for a specific patient should only be broken when information about the patient's protocol treatment is considered necessary to manage Serious Adverse Events (emergency unblinding). Unblinding procedures should preferably be initiated only after consultation of the principal investigator/coordinating investigator or his/her representative. To initiate an emergency unblinding the pharmacist on call for the VU University Medical Center should be contacted (see contact details chapter 4). The pharmacist on call will inform HOVON Data Center by e-mail about the emergency unblinding.

In addition non-emergency unblinding may be required in patients who are off protocol treatment in order to determine subsequent treatment regimens following progression. Unblinding procedures should only be initiated after consultation of the principal investigator/coordinating investigator or his/her representative.

16 Data collection and quality assurance

16.1 Case Report Forms

Data will be collected on Case Report Forms (CRF) to document eligibility, safety and efficacy parameters, compliance to treatment schedules and parameters necessary to evaluate the study endpoints. Data collected on the CRF are derived from the protocol and will include at least:

- Inclusion and exclusion criteria;
- Baseline status of patient including medical history and stage of disease;
- Timing and dosage of protocol treatment;
- Baseline concomitant diseases and adverse events;

- Parameters for response evaluation;
- Any other parameters necessary to evaluate the study endpoints;
- Survival status of patient;
- Reason for end of protocol treatment.

Each CRF page will be identified by a trial number, and a combination of patient study number (assigned at registration) and hospital identification.

The CRF will be completed on site by the local investigator or an authorized staff member. All CRF entries must be based on source documents. The CRF and instructions for completing the CRF will be provided by the HOVON Data Center.

The CRF pages must be made available to the HOVON Data Center at the requested time points as specified in the CRF instructions.

All data will be collected in the study database by the HOVON Data Center

16.2 Data quality assurance

Steps to be taken to ensure the accuracy and reliability of data include the selection of qualified investigators and appropriate study centers, review of protocol procedures with the investigator before the study, and site visits by the sponsor.

Data collected on the CRF will be verified for accuracy. If necessary, queries will be sent to the investigational site to clarify the data on the CRF. The investigator should answer data queries within the specified time line.

16.3 Monitoring

This trial is part of the HOVON Site Evaluation Visit program. Site evaluation visits will be performed for HOVON trials to review the quality of the site and not specifically the quality of a certain trial. It will enable HOVON to collect quality data and facilitate improvement of the participating sites. Data cleaning or monitoring of the performance of specific trials is not the goal of the site evaluation visits. Site evaluation visits will be performed according to the site evaluation visit plan.

The HOVON site evaluation visit plan applies to sites in the Netherlands only. Monitoring of the quality of trial conduct in participating sites from other countries will be organized by the coordinating investigator or co-sponsor. The frequency and content of the site visits in other countries will be at least equal to the specifications of the site evaluation visit plan, and are described in a monitoring plan provided by HOVON.

Direct access to source documentation (medical records) must be allowed for the purpose of verifying that the data recorded in the CRF are consistent with the original source data. The sponsor expects

that during site visits the relevant investigational staff will be available, the source documentation will be available and a suitable environment will be provided for review of study-related documents.

16.4 Audits and inspections

The investigator will permit site-visits to carry out an audit of the study in compliance with regulatory guidelines. These audits will require access to all study records, including source documents, for inspection and comparison with the CRFs. Patient privacy must, however, be respected. Similar auditing procedures may also be conducted by the manufacturer of ixazomib citrate (Millennium The Takeda Oncology Company) or by agents of any regulatory body reviewing the results of this study. The investigator should immediately notify the sponsor if they have been contacted by a regulatory agency concerning an upcoming inspection.

17 Ethics

17.1 Accredited ethics committee

An accredited Ethics Committee will approve the study protocol and any substantial amendment.

17.2 Ethical conduct of the study

The study will be conducted in accordance with the ethical principles of the Declaration of Helsinki, the ICH-GCP Guidelines, the EU Clinical Trial Directive (2001/20/EG), and applicable regulatory requirements. The local investigator is responsible for the proper conduct of the study at the study site.

17.3 Patient information and consent

Written informed consent of patients is required before enrolment in the trial and before any study related procedure takes place.

The investigator will follow ICH-GCP and other applicable regulations in informing the patient and obtaining consent. The investigator should take into consideration if the patient is capable of giving informed consent. Before informed consent may be obtained, the investigator should provide the patient ample time and opportunity to inquire about details of the trial and to decide whether or not to participate in the trial. All questions about the trial should be answered to the satisfaction of the patient.

There is no set time limit for the patient to make a decision. The investigator should inform each patient if there is a specific reason why he/she must decide within a limited time frame, for example if patients condition necessitates start of treatment or if the trial is scheduled to close for enrolment.

The content of the patient information letter, informed consent form and any other written information to be provided to patients will be in compliance with ICH-GCP and other applicable regulations and should be approved by the Ethics Committee in advance of use.

The patient information letter, informed consent form and any other written information to be provided to patients will be revised whenever important new information becomes available that may be relevant to the patient's consent. Any revised informed consent form and written information should be approved by the Ethics Committee in advance of use. The patient should be informed in a timely manner if new information becomes available that might be relevant to the patient's willingness to continue participation in the trial. The communication of this information should be documented.

17.4 Benefits and risks assessment.

The benefit will be that patients will be treated with a proteasome inhibitor/IMiD/corticosteroid based induction regimen, that has been shown to result in the highest response rates when compared non-head to head to European standard proteasome inhibitor/alkylating agent/corticosteroid or IMiD/alkylating agent/corticosteroid based regimens. Moreover, the oral proteasome inhibitor ixazomib citrate has been shown to induce considerably less neuropathy. The burden will be that following induction therapy, maintenance therapy will be given until progression. Although a benefit with respect to prolongation of PFS is expected, the extent is currently unknown. Patients may suffer from side effects, although these are generally mild with ixazomib citrate. Moreover, 50% of patients receive a placebo. There are no additional procedures required as compared to standard care. Patients will only be requested to participate in Quality of Life studies.

17.5 Trial insurance

Prior to the start of the trial, the sponsor will ensure that adequate insurance for patients is in place covering losses due to death or injury resulting from the trial, in accordance with applicable laws and regulations in each country where the trial is conducted. The sponsor will take out an insurance policy or delegate this responsibility to a national co-sponsor. Proof of insurance will be submitted to the Ethics Committee.

In addition, the sponsor will ensure that adequate insurance is in place for both investigator(s) and sponsor to cover liability pertaining to death or injury resulting from the trial.

18 Administrative aspects and publication

18.1 Handling and storage of data and documents

18.1.1 Patient confidentiality

Each patient is assigned a unique patient study number at enrolment. In trial documents the patient's identity is coded by patient study number as assigned at enrolment. In some cases date of birth is also listed.

The local investigator will keep a subject enrolment and identification log that contains the key to the code, i.e. a record of the personal identification data linked to each patient study number. This record is filed at the investigational site and should only be accessed by the investigator and the supporting site staff, and by representatives of the sponsor or a regulatory agency for the purpose of monitoring visits or audits and inspections.

18.1.2 Filing of essential documents

Essential Documents are those documents that permit evaluation of the conduct of a trial and the quality of the data produced. The essential documents may be subject to, and should be available for, audit by the sponsor's auditor and inspection by the regulatory authority(ies).

The investigator should file all essential documents relevant to the conduct of the trial on site. The sponsor will file all essential documents relevant to the overall conduct of the trial. Essential documents should be filed in such a manner that they are protected from accidental loss and can be easily retrieved for review.

18.1.3 Record retention

Essential documents should be retained for 15 years after the end of the trial. They should be destroyed after this time.

Source documents (i.e. medical records) of patients should be retained for at least 15 years after the end of the trial. Record retention and destruction after this time is subject to the site's guidelines regarding medical records.

18.1.4 Storage of samples

Biological samples should only be stored for the purpose of additional research if the patient has given consent. If no informed consent was obtained, samples should be destroyed after the patient has completed all protocol treatment and procedures.

Storage of biological samples on site is subject to the site's guidelines; samples may be labeled with the patients identifying information (e.g. name, hospital record number).

Samples that are shipped to another facility (e.g. a central laboratory) for a purpose as described in this protocol or for additional scientific research, should be stripped from any identifying information and labeled with a code (trial name or number and patient study number as assigned at enrolment).

18.2 Amendments

A 'substantial amendment' is defined as an amendment to the terms of the Ethics Committee application, or to the protocol or any other supporting documentation, that is likely to affect to a significant degree:

- the safety or physical or mental integrity of the patients of the trial;
- the scientific value of the trial;
- the conduct or management of the trial; or
- the quality or safety of any intervention used in the trial.

All substantial amendments will be submitted to the Ethics Committee and to the Competent Authority.

Non-substantial amendments will not be submitted, but will be recorded and filed by the sponsor.

18.3 Annual progress report

The sponsor will submit a summary of the progress of the trial to the accredited Ethics Committee once a year. The first report is sent one year after the first approval date of the trial. The last report is sent one year after the last patient has completed protocol treatment. Information will be provided on the date of inclusion of the first patient, numbers of patients included and numbers of patients that have completed the trial, serious adverse events/ serious adverse reactions, other problems, and amendments.

18.4 End of study report

The sponsor will notify the accredited Ethics Committee and the Competent Authority of the end of the study within a period of 90 days. The end of the study is defined as the last patient's last visit.

In case the study is ended prematurely, the sponsor will notify the accredited Ethics Committee and the competent authority within 15 days, including the reasons for the premature termination.

Within one year after the primary endpoint analysis of the trial, the sponsor will submit an end of study report with the results of the study, including any publications/abstracts of the study, to the accredited Ethics Committee and the Competent Authority. Upon request of the accredited Ethics Committee or the Competent Authority the sponsor will submit an updated version of the end of study report within one year after the last patient's last visit.

18.5 Publication policy

Final publication of trial results

Trial results will always be submitted for publication in a peer reviewed scientific journal regardless of the outcome of the trial – unless the trial was terminated prematurely and did not yield sufficient data for a publication.

The final publication of the trial results will be written by the Principal Investigator, the Co-investigators and the trial statistician on the basis of the statistical analysis performed by the trial statistician. A draft manuscript will be submitted for review to:

- ♦ All co-authors
- The chair of the relevant HOVON working group, who is entitled to share and discuss the manuscript with working group members
- The chair of NMSG, who is entitled to share and discuss the manuscript with working group members
- An industry partner if so agreed in the contract between HOVON and company

After revision the final manuscript is submitted to the HOVON secretary for review of compliance with this policy. After approval by the HOVON and NMSG boards the manuscript will be sent to a peer reviewed scientific journal.

Authorship

Authors of the main manuscript will include the Principal Investigator, the Co-investigators, investigators who have included more than 5% of the evaluable patients in the trial (by order of inclusion rate), the trial statistician and the trial manager. If a substantial part of the publication is based on centrally reviewed data (e.g. cytogenetics or pathology), the central reviewer will be included as author. Others who have made a significant contribution to the trial may also be included

as author, or otherwise will be included in the acknowledgement. A different strategy may be followed based on the specific criteria of the journal to which the manuscript has been submitted.

Authors of correlative manuscripts (e.g. results of side studies) will include the Principal Investigator, the Co-investigators, and those persons who have made a significant contribution to the published results.

The Principal Investigators should discuss and decide on the matter of authorship of the main manuscript prior to the start of the trial – with the exception of authors included on account of inclusion rate. The Principal Investigator is urged to use the maximum number of authors allowed by the journal to the full extent.

Interim and partial publications

Interim publications, abstracts or presentations of the study may include demographic data, overall results and prognostic factor analyses, results for secondary endpoints, but no comparisons between randomized treatment arms for the primary endpoint may be made publicly available before the recruitment is discontinued.

Investigators participating in the trial have a right to publish results from data they collected for the study. The Principal Investigator, the Co-investigator(s) and the trial statistician must approve any such publication, abstract or presentation based on patients included in this study. This is applicable to any individual patient or any subgroup of the trial patients. Such a publication cannot include any comparisons between randomized treatment arms nor an analysis of any of the study endpoints unless the final results of the trial have already been published.

Abstracts and presentations

Abstracts and presentations at public meetings will represent the trial as a project under HOVON and NMSG affiliations. The abstract or presentation should not be represented under affiliation of the working group or a specific hospital.

Slides will be designed using the HOVON and NMSG style template and any other presentation materials will show the HOVON and NMSG logos.

Prior to its public use, the abstract or presentation is submitted to the HOVON secretary for review of compliance with this policy.

Glossary of abbreviations

(in alphabetical order)

AE Adverse Event

AL Amyloid Light-chain

ANC Absolute Neutrophil Count

BJ Bence Jones BM Bone Marrow

Ca Calcium

CA Competent Authority
CBC Complete Blood Count
CR Complete Remission

CRAB Calcium elevation, Renal insufficiency, Anemia and Bone abnormalities

CRF Case Report Form CRP C-Reactive Protein

CTCAE Common Terminology Criteria for Adverse Events

DDI Drug Drug Interaction
DFS Disease Free Survival

DSMB Data Safety and Monitoring Board

DVT Deep Venous Thrombosis

ECG Electrocardiogram

FISH Fluorescence In Situ Hybridisation

FLC Free Light Chain

GCP Good Clinical Practice

G-CSF Granulocyte-Colony Stimulating Factor

GI Gastrol Intestinal
Hb Hemoglobin

HIV Human Immunodeficiency Virus

HOVON Dutch-Belgian Hematology-Oncology Cooperative Group

HRC Hematocytology Review Committee

ICH International Conference on Harmonization of technical requirements for registration of

pharmaceuticals for human use

IFE Immunofixation Electrophoresis
IFM Intergroup Français de Myelome

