14.1 Patient numbers and power considerations

There are no data yet on PFS after 9 cycles of ixazomib citrate – thalidomide – dexamethasone induction chemotherapy. However, in the recently published MPR-R trial (Palumbo et al, NEJM. 2012; 366: 1759-69), median PFS for no-maintenance *after MPR* was 7 months. If ixazomib citrate - thalidomide – low dose dexamethasone is a more effective induction regimen, median PFS after randomization in the no-maintenance arm may be 10 months. Median PFS for lenalidomide maintenance *after MPR* was 26 months. An improvement of median PFS from 10 to 26 months with ixazomib citrate-maintenance equals a hazard ratio of 0.39. For the current sample size calculation the following assumptions have been used:

- uniform accrual for 18 months; additional follow up of 12 months after the last patient has been randomized;
- two-sided significance level a = 0.05;
- power $1 \beta = 0.90$;
- median PFS in the no-maintenance arm = 10 months:
- HR = 0.39.

This results in a total number of patients to be randomized of 94 (= 47 per arm), and the final analysis will be performed when 55 events after randomization have been reported (using the Freedman-Peto method). If we assume that 66% (based on the 34% discontinuation rate in the VISTA trial) of the patients will be randomized, then 94/0.66 = 142 patients have to be registered. However, in case the randomization rate is lower then expected, we will recalculate the number of patients that have to be registered, in order to achieve 94 randomized patients required for the primary endpoint. An estimate of the randomization rate will be performed in the first 50 patients.

Assuming a response rate of about 80% after induction chemotherapy, the 142 registered patients will enable to estimate the response rate with a standard error of about 3%.

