14.2.1 Efficacy analysis

The main endpoint will be PFS from the date of randomization. The formal test for difference in PFS between the two treatment arms will be done with a multivariate Cox regression analysis with adjustment for International Scoring System (ISS, I vs II and III), age (<75 vs ≥ 75 years) and response after induction treatment ((s)CR vs VGPR and PR). An estimate of the HR with corresponding 95% CI will be obtained. The actuarial Kaplan-Meier method will be used to estimate PFS probabilities at appropriate time points, while the Greenwood estimate will be used to construct corresponding 95% CIs. Competing risk analysis will be used to calculate cumulative incidences of PFS, progression/relapse, and death without progression (which add up to 100% at every time point). A Kaplan-Meier curve will be generated to illustrate PFS in each arm. In case the accrual will be 18 months, randomization will take place 9 months after registration of the last patient, and if 12 months of follow up after the last patient is required, then the final analysis may be performed after 18 + 9 + 12 = 39 months after start of the trial, if the complete and validated data including 55 events are available. The response rate after induction chemotherapy will be summarized as the proportion of patients with at least a PR, together with a 95% CI.

A preliminary efficacy analysis on response after induction treatment is planned when the data regarding induction treatment and response of the first 50 registered and eligible patients are available and have been evaluated. No conclusions will be drawn based on this analysis.

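### The publication policy lifts the bar on by-arm PFS results when recruitment stops, 12 or 21 months before the planned 55-event analysis

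*Protocol*

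**What the plan says.** **Publication rule.** Under the heading on interim and partial publications in section 18.5, trial-level publications may report demographics, overall results, prognostic factor analyses and secondary-endpoint results, but "no comparisons between randomized treatment arms for the primary endpoint may be made publicly available before the recruitment is discontinued". The next paragraph concerns participating investigators who publish from data they collected. There the rule is stricter: "Such a publication cannot include any comparisons between randomized treatment arms nor an analysis of any of the study endpoints". That bar lifts only once the trial's final results are in print.

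**Timing of the primary comparison.** Section 14.1 assumes "uniform accrual for 18 months; additional follow up of 12 months after the last patient has been randomized" and states that "the final analysis will be performed when 55 events after randomization have been reported". Section 14.2.1 puts registration, induction and follow-up end to end: "then the final analysis may be performed after 18 + 9 + 12 = 39 months after start of the trial".

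**Error control and interim looks.** Section 14.1 sets a "two-sided significance level a = 0.05", with no division over looks. Section 14.3 plans one interim analysis, primarily to describe adverse events during induction, reported confidentially to the DSMB. Section 14.2.4 makes the primary analysis the only confirmatory one.

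**Blinding.** Maintenance runs until progression (section 9.2.1). Allocation is withheld from patients and caregivers until the end of the trial (section 15.2.2). Section 15.3 prefers unblinding after completion, with exceptions for emergencies and for patients who are off protocol treatment.

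**The concern.** The end of recruitment is the wrong milestone for this bar. Randomisation comes after about nine months of induction and the primary endpoint is event-driven, so recruitment stops long before the PFS comparison is mature. From then on the policy allows PFS to be shown publicly by arm while patients are still taking blinded capsules and most or many of the events are still to come.

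The secondary endpoints widen the gap. The by-arm restriction names only the primary endpoint, so results by arm for the others are not restricted even during recruitment. Section 13.2 lists PFS from registration and OS from randomisation. In randomised patients, PFS from registration shown by arm would rest on the same progressions and deaths as the primary endpoint.

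What is at stake is mainly conduct. Knowledge of an interim difference could change willingness to stay on blinded maintenance or prompt requests for unblinding, and so affect the remaining PFS and OS data. The two paragraphs of section 18.5 are also out of step: the looser cut-off applies to trial-level publications, which carry the full by-arm data.

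**Working it through.** **Inputs (sections 14.1 and 14.2.1).** Control median PFS 10 months; HR 0.39; 94 patients, 47 per arm; two-sided alpha 0.05; power 0.90; 18 months of uniform accrual; last randomisation 9 months after last registration; 12 further months of follow-up. Exponential PFS is assumed.

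**1. Reproduce the plan's figures.**
- Freedman events: (1.960 + 1.282)² × [(1 + 0.39)/(1 − 0.39)]² = 10.51 × 5.19 = 54.6, rounded up to 55. This agrees with the Protocol.
- Hazards: control λ₀ = ln 2/10 = 0.0693 per month; ixazomib λ₁ = 0.39 × 0.0693 = 0.0270.
- Probability of an event with uniform entry over *a* months and *F* further months: p = 1 − [exp(−λF) − exp(−λ(a + F))]/(λa).
- With a = 18 and F = 12: p₀ = 0.751, p₁ = 0.428, mean 0.589. Then 55/0.589 = 93.3, or 94 patients. This also agrees.

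**2. When the bar ends.** Registration closes at month 18. The last randomisation is at month 18 + 9 = 27. The final analysis is at month 27 + 12 = 39.
- Recruitment read as registration: 39 − 18 = 21 months early.
- Recruitment read as randomisation: 39 − 27 = 12 months early.

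**3. Expected events at each date,** with randomisation uniform over months 9 to 27:

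| Month | Randomised | p₀ | p₁ | Events | Share of 55 |
|---|---|---|---|---|---|
| 18 | 47 | 0.256 | 0.112 | 23.5 × 0.368 = 8.7 | 16% |
| 27 | 94 | 0.429 | 0.208 | 47 × 0.637 = 29.9 | 54% |
| 39 | 94 | 0.751 | 0.428 | 47 × 1.179 = 55.4 | 101% |

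**4. Conditional type I error.** Suppose an early comparison at |Z| > 1.96 were counted as a positive finding in addition to the final test. Z-statistics at two looks have correlation equal to the square root of the ratio of their event counts: √(29.9/55) = 0.74 for month 27 against the final analysis, and √(8.7/55) = 0.40 for month 18 against the final analysis. Simulation (4 million draws) gives the chance of at least one false positive:
- month 27 and final: 8.2%
- month 18 and final: 9.3%
- months 18, 27 and final: 11.9%

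The planned figure is 5%.

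**The case against.** The strongest reply is that the clause is only a minimum prohibition. It schedules no early comparison, and nothing else in the Protocol does: PFS is formally tested once, the interim analysis concerns induction safety, and the early response look in section 14.2.1 covers induction only. This stands. The finding is about what the policy permits.

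A reader might infer that the clause raises the type I error of the trial to 8–12%. The documents do not support that. No rule declares success at a public look, and section 14.2.4 treats everything except the primary analysis as hypothesis-generating. A released estimate that triggers no stopping and no claim does not in itself alter the rejection rule of the final test.

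A reader might also infer that results could certainly come out while half of the patients are still to be randomised. That holds only if recruitment means registration, and section 18.5 does not say so. On the other reading all 94 are already randomised.

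The bias route is also limited. Aggregate results do not reveal an individual's allocation; section 15.3 already allows unblinding after protocol treatment ends so that later therapy can be chosen; and progression rests largely on laboratory thresholds confirmed at two assessments (Appendix C). These points reduce the risk but do not remove it, since withdrawal from blinded maintenance remains plausible and cannot be quantified from the documents.

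Abstracts are reviewed by the HOVON secretary, so release is not without oversight. But that review checks compliance with this same policy, which an early by-arm comparison would satisfy.

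**Conclusion.** The point holds as a wrongly chosen milestone in a stated rule. The bar on by-arm primary-endpoint results ends 12 months (randomisation reading) or 21 months (registration reading) before the planned analysis, with about 30 or about 9 of the 55 events observed. It sits badly with the blinding in sections 15.2.2 and 15.3 and is looser than the neighbouring rule for investigators' publications. By-arm secondary results that share the primary events or follow randomisation are not restricted at all.

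The dates and counts rest on the Protocol's own assumptions: accrual on schedule, nine months from registration to randomisation, exponential PFS, a 10-month control median and HR 0.39. If events come more slowly than planned, the gap widens. The harm is a possible effect on conduct if the sponsor chooses to release early; the 8% and 12% figures apply only if such a release is also read as a positive result. Because the clause changes no endpoint, sample size or analysis, this is a cheap improvement that should be made. It does not invalidate the design.

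**What to change.** In section 18.5, replace the end of recruitment as the cut-off for trial-level publications by completion of the final PFS analysis at 55 events. The cut-off already used in the next paragraph, publication of the final results, would also serve. Apply the same cut-off to by-arm results for every endpoint assessed after randomisation, including OS from randomisation and PFS from registration when shown by arm. State that pooled results and induction results may still be published early.

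This is a change of one sentence plus a short extension. It also removes the need to define recruitment for this purpose. The only cost is that by-arm abstracts appear later.
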